cortex impairs spatial working memory [39]. Norepinephrine appears to play a role in spatial working memory formation [38] as well as attentional set-shifting [37,38]. Acetylcholine has been implicated in aspects of reversal learning in the orbitofrontal cortex [37]. Furthermore, behavioral studies in humans suggest that acetylcholine is responsible for maintenance of attention and increased levels of this neurotransmitter are related to attentional effort [40]. Finally, histamine seems to affect learning and memory, partly via modulating acetylcholine release [41]. In rats, blockade of 113 receptors improves social memory, enhances attention and improves cognitive performance. Cetirizine, an H1 receptor antagonist, impairs memory processing speed [42; data on file with Takeda].

Vortioxetine is a novel antidepressant with hypothetical multimodal mechanism of action. It is thought to work through a combination of multiple pharmacological modes of action: 5-HT reuptake inhibition, 5-HT3 and 5-HT7 receptor antagonism, 5-HT1A receptor agonism, and 5-HT1B receptor partial agonism [43]. In vivo nonclinical studies have demonstrated that vortioxetine enhances levels of the neurotransmitters 5-HT, NE, DA, acetylcholine and histamine in specific areas of the brain [43]. These affinities are all considered to be of clinical relevance and involved in the mechanism of action at therapeutic doses.

Vortioxetine showed antidepressant activity in completed MDD studies in which primary endpoints were change in depressive symptoms. Currently, three placebo-controlled clinical trials demonstrate vortioxetine's efficacy on cognitive performance in adult outpatients with MDD (Katona, et al., 2012; McIntyre, et al., 2013; data on file with Takeda). Two of the above studies (Katona, McIntyre) included duloxetine as a comparator antidepressant; both active antidepressants demonstrated antidepressant efficacy compared to placebo. Vortioxetine, not duloxetine, showed improvement compared to placebo on the Digit Symbol Substitution Test (DSST). Results of these two studies also suggested that the improvement with vortioxetine (and not duloxetine) was a result of direct effects versus indirect (via mood) improvement in cognition. Correlating the clinical changes in mood and cognition with translational imaging data could provide insight to diagnose and manage cognitive changes associated with MDD.

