#### **Rationale for the Proposed Study:**

Vortioxetine has been shown to improve core depressive symptoms and improve cognitive function in adult outpatients with MDD and subjective complaints of cognitive function. This pilot study is intended to evaluate the extent to which BNA technology can provide clinically valuable information and provide information toward designing a subsequent confirmatory study that will further elucidate the effect of vortioxetine on MDD and cognitive function in this population. This exploratory study will ascertain the acute changes in core depression symptoms, cognitive function, tolerability, and safety using flexible-dose vortioxetine in adult outpatients with MDD with subjective complaints of cognitive functioning, as measured by BNA changes and standard outcome measures for depression and cognition.

Data suggest that the impact of vortioxetine on cognition in MDD may be independent of the antidepressant effect, perhaps through a centrally-mediated pathway different from that involved in the antidepressant effects. This study will investigate the effect of vortioxetine on cognitive dysfunction more broadly covering specific measures of attention, executive functioning and psychomotor speed, as well as assess its effect on core depressive symptoms, function and global change. The number of subjects treated in this study is generally accepted for exploratory studies and intended to demonstrate 1) improvement in cognition and efficacy in conventional MDD symptom domains, 2) improvement in cognition but no antidepressant efficacy in conventional MDD symptom domains, and, 3) no improvement of cognition and no antidepressant efficacy in conventional MDD symptom domains. We predict distinct patterns in brain network activity among these subgroups. This preliminary data is expected to provide greater insight into understanding the direct versus indirect antidepressant effects

of acute treatment with vortioxetine on cognition in MDD, and provide a basis for future clinical trials and applications.

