    - i. Subjects meeting antidepressant efficacy criteria (based on response and remission criteria for MADRS, HRSD, QIDS) and improvement in cognition (based DSST).
    - ii. Subjects failing to meet antidepressant efficacy criteria (based on response criteria for MADRS, HRSD, QIDS) but show improvement in cognition (based on DSST).
    - iii. Subjects failing to meet antidepressant efficacy criteria (based on response criteria for MADRS, HRSD, QIDS) and failing to show improvement in cognition (based on DSST).
    - iv.
    - v.
- 5. To explore changes in BNA patterns in MDD with cognitive dysfunction prior to receiving treatment with vortioxetine and:
  - a. Severity of MDD as measured by baseline MADRS total score, QIDS-SR-16 total score, HDRS-28 item total score and CGI-Severity.
  - b. Severity of cognition dysfunction and functionality as measured by baseline DSST, TMT-A/B, TMT-B, Stroop, MGH-CPFQ total score, UPSA, WLQ.
  - c. Prediction of achieving symptomatic remission of MDD as measured by remission status on MADRS total score, HDRS-17 total score and CGI-Improvement (1 or 2)
  - d. Prediction of cognitive improvement measured by DSST score; cutoff 70% improvement from baseline.
- 6. Explore relationship with changes in BNA patterns in remitted vs. non-remitted subjects after 8 weeks of treatment with vortioxetine as measured by MADRS total score, HDRS-17 total score, QIDS total score,, and CGI-Improvement.
- 7. Assess safety and tolerability of 8 weeks open-label, flexible-dose vortioxetine in all subjects for:
  - a. Spontaneously reported adverse events
  - b. Clinical safety laboratory tests (when indicated, vital signs, weight, EKGs and physical exam)

- c. Evaluate relationship between adverse events after 2 and 8 weeks of treatment with changes in BNA patterns for nausea, worsening of baseline suicidal ideation (as measured by MADRS item 10, HDRS-17 item 2 and C-SSRS)

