## **STATISTICAL ANALYSES**

### **Primary Efficacy Analysis**

The primary endpoint is the change from Baseline in the MADRS and DSST score. The primary endpoint will be analyzed using analysis of covariance (ANCOVA), with treatment and center as fixed factors, and baseline score as covariate. The p-values, least squares (LS) treatment means, difference between the LS treatment means, and 95% CIs for the treatment differences will be displayed.

This is a pilot study that is intended to evaluate the extent of to which BNA technology can provide clinically valuable information, and to provide data that will help design a future confirmatory study. Because this is an exploratory study, no formal sample size calculation was performed; rather, sample size has been based on that which is generally accepted by the medical community for a study of this nature. In order to strengthen the level of confidence of the results, the BNA test is performed twice before the subject is given medication to provide repeatability and two additional times during the course of treatment to allow the identification of any potential trend that may occur as a result of treatment.

The relationship between changes in BNA and BNA total mean change from baseline and endpoint will be analyzed. Changes in BNA from baseline will also be analyzed by groups defined on endpoint status (e.g. response to MADRS, remission, change in DSST).

Statistical analysis should also consider the fact that changes in brain networks may be independent of symptoms or neurocognitive scores; thus, the analysis of BNA changes across treatment duration should be also performed independently. In other words, it is possible that BNA conveys information that is not found in other methods; trying to find correlations may limit the correct interpretation. Therefore, robust trends found in BNA scores should be further researched, regardless of finding correlations to symptoms or neurocognitive tests. For example, it could be that a change in BNA, without a significant change in symptoms, means that if the treatment will be continued for a few more weeks, a delayed improvement will be found; etc.

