### **Secondary Efficacy Analyses**

Change from Baseline in TMT A, TMT B, , PDQ, MGH-CPFQ, UPSA, percentage of productivity loss (WLQ), MADRS, CGI-S, and CGI-I will be analyzed at all time points (where rated) using ANCOVA model similar to the one described above for the primary endpoints.

MADRS responders (defined as a >50% decrease from Baseline), MADRS remission (defined as a MADRS total score <10). CGI-S remission (CGT-S2), and CGI-I response (CGI-I2) will be analyzed at all time points by logistic regression, adjusting for baseline score and treatment.

Proportion of cognitive dysfunction improvement that is not due to an improvement in depressive symptoms will be analyzed using a path analysis with change from Baseline in DSST score and change from Baseline in MADRS total score as endogenous variables.

C-SSRS will be summarized at all time points using descriptive techniques.

All statistical tests will be 2-sided and at the 5% level of significance. Ninety-five percent confidence limits will be presented together with the p-values.

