**Antidepressant medication (vortioxetine)**

At the time of informed consent, the subject will be instructed about the risks and benefits of the vortioxetine that will be used throughout the study.

The potential risks of the medication will be based upon the FDA-approved package insert labeling for vortioxetine and will include, but not limited to, spontaneous reported adverse events and potential serious adverse events. Source documents will contain documentation that the subject was informed of risks of treatment and that there was adequate time to read and discuss this information with the clinician during the informed consent process.

The FDA-approved package insert for vortioxetine recommends a starting dose of 10 mg/day, increased to 20 mg/day as tolerated. The maximum dose is 20 mg/day, and the minimum dose is 5 mg/day if a higher dose is not tolerated. This allows for individualized “flexible” dosing for efficacy and tolerability.

In order to standardize this flexible dosing, all subjects will be started at 10 mg/day following visit 2 (baseline). The dose will be increased to a maximum of 20 mg/day after visit 4 (2 weeks of treatment) if tolerated by the subject. Dose decreases may occur at any time until Visit 8 for tolerability issues, to a minimum dose of 5 mg/day, and the dose may be re-increased if the tolerability issue resolves.

No dose adjustments may take place after visit 8 through the end of treatment (Visit 10).

Safety, tolerability, and depressive symptoms/function assessments will occur at baseline and each subsequent visit through the end of the study. While this is an exploratory analysis, the impact of treatment at various points in the study will be analyzed. Baseline assessments will occur prior to the subject receiving medication.

Drug accountability will be recorded at all visits. Subjects failing to meet at least 80% adherence to study medication between study visits will be discontinued from the study.

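### Without a comparator, the planned path analysis cannot separate a mood-independent drug effect on the DSST from retest and time gains

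*Combined protocol and SAP*

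**What the plan says.** Under Secondary Efficacy Analyses the plan states: "Proportion of cognitive dysfunction improvement that is not due to an improvement in depressive symptoms will be analyzed using a path analysis". The only model variables it names are the changes in DSST and in MADRS, and both are treated as endogenous. It names no exogenous variable, gives no formula for the proportion and sets no limit on its interpretation.

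The design has one arm. Secondary outcome 7 reads: "Assess safety and tolerability of 8 weeks open-label, flexible-dose vortioxetine in all subjects". The section on the antidepressant medication starts every subject on the same dose, and later variation is clinical: "Dose decreases may occur at any time until Visit 8 for tolerability issues". The primary ANCOVA is specified "with treatment and center as fixed factors, and baseline score as covariate", but treatment has a single level here.

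Appendix I marks the DSST at screening and at Visit 10 (or early termination) only. The Primary Efficacy Analysis section describes a repeat measurement before treatment for the BNA, not for the DSST.

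The Introduction reports, from earlier placebo-controlled trials, that "the improvement with vortioxetine (and not duloxetine) was a result of direct effects versus indirect (via mood) improvement in cognition". The Rationale then says of the present study: "This preliminary data is expected to provide greater insight into understanding the direct versus indirect antidepressant effects".

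**The concern.** To split a drug's effect on cognition into a part through mood and a part not through mood, one must first have an effect of the drug. That means a contrast between treated and untreated subjects, or between randomised doses. The cited trials had placebo arms; this study has none. Adding center or baseline score to the path model does not create a contrast. Nor does dose, which follows tolerability and is not randomised.

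What remains is the DSST change that does not track MADRS change. That residue holds any direct drug effect, but also practice on a repeated timed test, time, and possibly regression to the mean, since subjects scoring 70 or more on the DSST are excluded. The slope on MADRS change is itself an association and need not be causal.

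At stake is a single percentage that reads like a mechanistic result. Given the Rationale, it could be taken as evidence of a mood-independent effect of vortioxetine when practice of the same size would produce it. The study is also meant to inform a confirmatory trial, and at 40 subjects the figure is too imprecise for that use.

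**Working it through.** The plan states no expected share, effect size or SD, so there is no figure to reproduce. The check is algebra first, then simulation for size.

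**Model.** For subject i, with M the MADRS improvement:

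DSST change = r + d + b·M + error,

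where r is retest and time gain, d is the direct drug effect and b is the slope on mood. In one arm, r and d are both constants, so only the intercept a = r + d can be estimated. The plan gives no formula. One natural version of the share is

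S = a / (a + b·m), with m the mean MADRS improvement.

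r and d enter S only through their sum.

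**Inputs.** From the documents: n = 40. Assumed: m = 15, SD of M = 9, residual DSST SD = 7, and a mood-linked gain b·m of 3 symbols, so b = 3/15 = 0.2. Each scenario used 40,000 simulated trials; medians vary by up to 1 point between runs.

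**1. Practice versus drug.** Non-mood gain of 4 symbols, so S = 4/(4+3) = 57%.

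| r (practice) | d (drug) | Median share | 95% of trials |
|---|---|---|---|
| 4 | 0 | 57% | -6% to 111% |
| 2 | 2 | 58% | not listed |
| 0 | 4 | 57% | -6% to 112% |

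The agreement is guaranteed by the algebra; the simulation adds the spread.

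**2. No direct drug effect, practice varied.**

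| r | S = r/(r+3) | Simulated median | 95% of trials |
|---|---|---|---|
| 0 | 0% | 0% | -323% to 136% |
| 2 | 40% | 40% | -63% to 116% |
| 4 | 57% | 58% | -6% to 111% |
| 6 | 67% | 67% | 20% to 109% |

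In a separate run of 20,000 trials per scenario, the intercept differed from zero at the two-sided 5% level in 14%, 43% and 76% of trials for r = 2, 4 and 6. Those are correct rejections of a zero intercept, but with d = 0 none reflects a drug effect.

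**3. Precision.** The standard error of the intercept is about 7 × √(1/40 + 15²/(39 × 9²)) = 7 × √(0.025 + 0.0712) = 2.2 symbols, against an intercept of 4. In the all-practice case with r = 4, the 95% range of the share is 14% to 96% at residual SD 5 and -42% to 136% at SD 10.

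**4. Measurement error in MADRS change.** Let all gain be mood-linked (r = d = 0, true share 0%) and let MADRS change have reliability λ. The slope shrinks to λb, the intercept becomes (1 - λ)·b·m, and the share tends to 1 - λ: 20% at λ = 0.8 and 40% at λ = 0.6. Simulated medians were 20% and 41%. The spread is very wide: in the separate run at λ = 0.8, the median was 21% and 95% of trials lay between -256% and 145%.

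**5. Sensitivity to the mood-linked gain.** With r = 4, a mood-linked gain of 1 gives 4/5 = 80% and a gain of 6 gives 4/10 = 40%.

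**6. What a contrast would do.** In a hypothetical 20/20 design with mean MADRS improvements of 15 and 11, the mood-adjusted treatment coefficient averaged 0.04 and -0.03 when d = 0 with r = 3 and 6. It averaged 3.0 when d = 3 with r = 0. A comparator therefore separates d from r, provided nothing unmeasured confounds mood and cognition. With 20 per arm the estimates still ranged about ±4.5 symbols around the truth.

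**The case against.** The strongest reply is that the plan speaks of improvement not due to mood, and does not say due to vortioxetine. Practice and time legitimately belong to that remainder. The Rationale's direct-versus-indirect sentence follows a description of response subgroups and their BNA patterns, and it does not mention the path analysis. The study calls itself an exploratory pilot, and 95% limits are promised, which would expose the imprecision. No document says that this share will feed the design of the next trial. The simulated estimator is one choice among several, and its inputs are assumed.

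Part of this stands. The simulation only illustrates size, a single-arm share can be computed, and the analysis is secondary. The proposed slope also shares the attenuation and the non-causal status of the share.

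The rest does not remove the problem. Exploratory status excuses imprecision, but this question stays unanswerable at any sample size. The wording is causal, and even on the literal reading the share is biased, because the slope is associational and attenuated. The Introduction and Rationale supply the drug interpretation, and nothing in the plan warns against it. A slope reported as an association claims less than a proportion attributed to a cause.

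One further point: the exclusion criteria apply a DSST cut-off at the Baseline Visit, although Appendix I marks no DSST there. If one is given, two pre-treatment scores would allow a short-interval retest estimate. They would not cover eight weeks of other change, and the plan makes no such use of them.

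**Conclusion.** The concern holds. It follows from the single-arm design and does not depend on the assumed values: retest and time gain and any direct drug effect appear only as a sum. Under the stated assumptions, practice of 2 to 6 symbols with no direct drug effect gives a median share of 40% to 67%, and measurement error alone gives about 20% to 40% where the true share is zero. At 40 subjects the 95% range of the share spans more than 100 percentage points in most scenarios. Those sizes would change with other inputs; the lack of identification would not. This should be fixed before the percentage is computed or reported. It concerns a secondary analysis and does not touch the primary outcome.

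**What to change.** In Secondary Efficacy Analyses, replace the proportion with a descriptive analysis: the slope and partial correlation of DSST change on MADRS change, adjusted for baseline DSST and center, each with a 95% CI. The intercept may be shown if it is labelled as including practice and time effects. Add a sentence stating that direct and indirect drug effects on cognition cannot be separated in this single-arm study and are left to the controlled follow-up. Limit the direct-versus-indirect wording in the Rationale to match.

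Keeping the percentage, relabelled as the share of pre-post DSST change not statistically associated with MADRS change, would remove the drug attribution. It would leave the attenuation and the imprecision, so it is second best.

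The cost is wording in two sections, with no new data or visits. What is lost is a mechanistic percentage that the design cannot support.

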### Number of Subjects:

40 subjects enrolled. For purposes of IRB reporting, an enrolled subject is one who signs informed consent. For purposes of data analysis and reporting to the funding organization, an enrolled subject is one who meets all inclusion criteria and no exclusion criteria and completes the baseline visit including the baseline BNA.

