**APPENDIX I - SCHEDULE OF EVENTS**

Visit #	Screen 1	Baseline 2	3	4	5	6	7	8	9	10 (or ET)
Day	-2 to -14	0	7	14	21	28	35	42	49	56
Week	-1 to-2	0	1	2	3	4	5	6	7	8
Informed Consent	X									
Incl/Excl Criteria	X	X								
MINI	X									
ASRS	X									
Medical and Psychiatric History	X									
Demographics	X									
Physical Exam	X									
Laboratory tests, urinalysis, urine pregnancy test and urine drug screen 	X									
Vital signs and weight 	X	X	X	X	X	X	X	X	X	X
Height		X								
12-Lead ECG	X									
HDRS (28-item)	X	X	X	X	X	X	X	X	X	X
QIDS-SR-16	X	X	X	X	X	X	X	X	X	X
MADRS	X	X	X	X	X	X	X	X	X	X
DSST	X									X
UPSA	X									X
TMT-A AND TMT-B	X									X
Stroop Test	X									X
MGH-CPFQ	X	X	X	X	X	X	X	X	X	X
PDQ	X	X	X	X	X	X	X	X	X	X
CGI-S	X	X	X	X	X	X	X	X	X	X
CGI-I			X	X	X	X	X	X	X	X
WLQ	X	X	X	X	X	X	X	X	X	X
C-SSRS 	X	X	X	X	X	X	X	X	X	X
Concomitant therapy	X	X	X	X	X	X	X	X	X	X
Study drug dispensed		X	X	X	X	X	X	X	X	
Study drug accountability			X	X	X	X	X	X	X	X
Adverse events	X	X	X	X	X	X	X	X	X	X
EEG (BNA reading)	X	X		X						X

may be repeated at investigator's discretion

including body temperature (oral), blood pressure and pulse.

C-SSRS lifetime version at screen only; Since Last Visit version at V2-10

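### Treating observed MADRS change as error-free in the path analysis probably overstates the share of DSST gain not due to mood

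*Combined protocol and SAP*

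**What the plan says.** Under Secondary Efficacy Analyses, the plan states: "Proportion of cognitive dysfunction improvement that is not due to an improvement in depressive symptoms will be analyzed using a path analysis". The model is specified only as one "with change from Baseline in DSST score and change from Baseline in MADRS total score as endogenous variables". No visit, exogenous variable, formula for the share, latent mood variable or correction for rating error is given. The same section adds: "All statistical tests will be 2-sided and at the 5% level of significance", and asks for 95% limits alongside p-values.

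The Number of Subjects section reads "40 subjects enrolled", and the Primary Efficacy Analysis section says that "no formal sample size calculation was performed". There is one open-label arm.

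Appendix I schedules MADRS, the 28-item HDRS (whose first 17 items give HDRS-17) and QIDS-SR-16 at every visit from screening to Visit 10. It schedules DSST only at screening and Visit 10, whereas the exclusion criteria refer to a DSST score at the Baseline Visit.

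**The concern.** The analysis is meant to separate cognitive gain that follows mood from gain that does not. The mood variable is a rated scale, and a change in a rated scale contains error at both ends. Error in an explanatory variable flattens its slope. It leaves the mean change alone, provided the errors average zero in the patients analysed. A flatter slope assigns less of the DSST gain to mood, and the remainder is reported as not due to mood.

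The usual direction of this error favours the trial's own hypothesis. The Introduction cites two earlier studies as suggesting that the vortioxetine improvement "was a result of direct effects versus indirect (via mood) improvement in cognition", and the Rationale says the cognitive effect may be independent of the antidepressant effect. A moderate non-mood share could therefore be read as support when part or all of it comes from rating error. Confidence limits do not reveal this, because the estimate and its limits shift together.

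**Working it through.** The plan gives no share, reliability, effect size or SD, so there is no stated figure to reproduce. The inputs below marked *assumed* are not in the documents.

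**1. The share in one arm.** The natural reading is a regression of DSST change on MADRS change:

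share = 1 − slope × (mean MADRS fall) / (mean DSST gain).

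**2. Effect of independent rating error.** Let λ be the reliability of the MADRS change score. The slope is multiplied by λ, so

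reported share = 1 − λ × (1 − true share).

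| λ (*assumed*) | True share 0 | True share 0.50 |
|---|---|---|
| 0.8 | 1 − 0.8 = 0.20 | 1 − 0.8 × 0.5 = 0.60 |
| 0.7 | 1 − 0.7 = 0.30 | 1 − 0.7 × 0.5 = 0.65 |
| 0.6 | 1 − 0.6 = 0.40 | 1 − 0.6 × 0.5 = 0.70 |

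The upward shift is 20 to 40 points when the true share is zero and 10 to 20 points when it is 0.50. In terms of error size: with a true-change SD of 8 and rating error SD of 4 at each end (*assumed*), λ = 64 / (64 + 2 × 16) = 0.67. A true share of 0.50 is then reported as 1 − 0.67 × 0.5 = 0.67.

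**3. The entry cut.** Inclusion requires MADRS of at least 26, and Appendix I rechecks eligibility at baseline. Selecting on the rating that also starts the change score inflates the mean fall and gives some share back to mood. In simulation with true share zero, a baseline cut lowers 0.20, 0.30 and 0.40 to about 0.16, 0.24 and 0.33 (*assumed* true baseline mean near 30, true fall 15, SD 8). A cut at screening alone leaves them unchanged. With true share 0.50, error SD 4 and true baseline mean 27, the baseline cut reverses the bias: the share is 0.44 for a true fall of 3 (SD 8) and 0.49 for a fall of 8 (SD 12).

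**4. Error shared with DSST.** Suppose each point of Visit 10 MADRS error also lowers that day's DSST by 0.5 points (*assumed*; fall 15, SD 8, DSST gain 8, error SD 4, true share 0.50). The true slope is 0.5 × 8/15 = 0.267. The fitted slope is (0.267 × 64 + 0.5 × 16) / 96 = 0.261, and the share is 1 − 0.261 × 15/8 = 0.51, so the bias almost cancels. Adding the baseline cut gives 0.46 in simulation.

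**5. Sampling spread at n = 40.** With true share 0.50, error SD 4 and DSST residual SD 7 (*assumed*), the median estimate is 0.67. The central 95% runs from 0.17 to 1.10, and 7% of estimates exceed 1.

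**6. What a three-scale composite achieves (true share 0).** With equal reliabilities and independent errors, the share is 1 − 3λ/(1 + 2λ) = 0.08, 0.13 and 0.18 at λ = 0.8, 0.7 and 0.6. If MADRS and HDRS errors correlate at 0.8 (*assumed*), put v = (1 − λ)/λ = 0.25, 0.429 and 0.667. The error variance of the average is v × (3 + 1.6)/9 = 0.128, 0.219 and 0.341 per unit of true variance. The share is 1 − 1/(1 + that value) = 0.11, 0.18 and 0.25.

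**7. Centring.** The share in step 1 uses the mean of the mood variable. Ordinary z-scores have mean zero, so the mood part is zero and the share is 1 − 0 = 100%, whatever the data. Dividing by the SD without subtracting the mean avoids this.

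**The case against.** The strongest case against giving this weight is that rating error is not what most limits this analysis. With one arm, treatment is a constant, so the non-mood share also collects practice and time effects. At 40 patients the spread in step 5 exceeds the bias, and the required confidence limits would show it. Both points stand. They mean the share should be treated as descriptive, but they do not remove a shift that the limits cannot show.

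Other objections stand in part:

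- Keeping the rater consistent and covering inter-rater reliability at start-up reduce rating error without removing it.
- The plan does not say that a single rating is used at each end. That is an inference from the DSST schedule.
- A composite brings in content close to DSST. The protocol says HDRS rates psychomotor retardation, DSST assesses psychomotor speed, and QIDS-SR-16 covers every DSM-IV-TR symptom domain. MADRS already has a concentration item. This overlap could push the share down for the wrong reason, so the composite should not simply replace MADRS.

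A reader might infer that the bias always runs upward. Steps 3 and 4 show that this is not assured under the trial's own entry rule. A reader might also infer that a direct share will be reported whenever none exists. Take n = 40, λ of 0.6 to 0.8, mean MADRS fall 15 (observed SD 9), DSST gain 5 and residual SD 5 to 7, all assumed, with no true direct share. The estimate is then zero or negative in 11% to 32% of trials, and the direct part is significantly positive in 6% to 22%. That is above the nominal 2.5% but far from certain.

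**Conclusion.** The point holds as a modest, worthwhile improvement. The plan uses observed MADRS change without allowing for rating error, and such error tends to raise the non-mood share. For reliabilities of 0.8 to 0.6 the rise is about 20 to 40 points if all gain is mood-related and 10 to 20 points if half is. These sizes rest on an assumed reliability, on a regression form that the plan does not spell out, and on error independent of DSST.

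The direction is probable, not fixed. In the illustrations, selection alone reversed it only when the true MADRS fall was small or very variable. Strongly shared error cancelled it, and reversed it when combined with the entry cut.

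The documents do not support two further inferences. Nothing says that this share will set the design of the confirmatory study; the pilot is meant to inform that study in general terms. And correcting for rating error would not make the share a direct effect of vortioxetine, because the one-arm design remains.

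**What to change.** Keep the MADRS path analysis and add the following to the SAP:

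- State the path model, the formula for the share, and the visits that define each change score. Reconcile Appendix I with the exclusion criterion on when the pre-treatment DSST is taken.
- Report beside the MADRS result a sensitivity analysis with a multi-scale mood variable from the same visits. This can be the average of MADRS, HDRS-17 and QIDS-SR-16 change, each divided by its SD and not mean-centred, or a latent mood variable with a mean structure.
- Leave out the concentration and psychomotor items that overlap with DSST, or show the result with and without them.
- Give both shares with 95% confidence limits, label them descriptive, and say that the MADRS-only share is probably biased upward by rating error.

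The cost is some SAP wording and analysis time, with no new data. The correction is only partial if MADRS and HDRS rater errors are correlated (step 6), and the composite is less familiar than MADRS alone. Practice and time effects stay in the share either way.
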